7.2 Expected Toxicities

Pembrolizumab will be given per standard of care and toxicity information is available from phase III data. Full prescribing information for pembrolizumab can be found at: https://www.merck.com/product/usa/pi_circulars/k/keytruda/keytruda_pi.pdf.

Neutron radiation will also be given per standard of care at palliative dosing, which is generally well tolerated. Exact toxicity depends on site of treatment and typically includes fatigue and dermatitis in the treatment field.

The grade and severity of the event will be determined using CTCAE v.4.0. The event will be determined to be expected or unexpected. The determination of whether an AE is expected is based on pembrolizumab-specific adverse event information per prescribing information, as well as site specific toxicity listed on radiation treatment consent form for patients receiving radiation treatment. Unexpected AEs are those not listed in the agent-specific adverse event information nor radiation consent form. The event will be evaluated for relationship to the medical treatment or procedure. The Investigator should document his/her opinion of the relationship of the event to study medication as follows:

- Unrelated- The adverse event is clearly not related to the investigational agent(s).
- Possible-The adverse event may be related to the investigational agent(s).
- Probable-The adverse event is most likely related to the investigational agent(s).
- Definite- The adverse event is clearly related to the investigational agent(s).

Based on this information, institutional guidelines will be followed regarding whether an adverse event should be reported as an expedited report in addition to the routinely reported clinical data.

8 Data and Safety Monitoring Plan

Oversight for this study will be provided by the Principal Investigator with delegation of appropriate responsibilities to sub-investigators and designated study personnel. They will ensure all entry criteria are met prior to the initiation of the protocol and all study procedures and reporting of adverse events are performed according to the IRB-approved protocol.

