3.1 General Design

This is a study to test whether densely ionizing, high relative biologic equivalence (RBE) radiation in the form of neutron radiation, can improve the response rate to checkpoint inhibitor immunotherapy in patients with advanced urothelial carcinoma. In this trial, the addition of focal radiation is hypothesized to act as a “vaccine” by releasing tumor neoantigens, with the goal being to augment the immune response. Trial schema is shown below in Figure 1 and study calendar in Table 1. Patients with advanced urothelial carcinoma about to receive checkpoint inhibitor therapy (pembrolizumab), with at least two sites of measurable disease per RECIST 1.1, will undergo neutron radiation to 1-3 sites of disease. At least one site of RECIST 1.1 evaluable disease must remain untreated³¹, as only non-radiated sites will serve as index lesions to assess for response rate per iRECIST criteria.³⁰ Asymptomatic lesions are eligible for radiation as the primary goal of the radiation therapy is to induce an immune response.

[figure not shown]

Figure 2. Clinical trial schema.

Table 1. Study Calendar.

	Pre-treatment⁴	Between Dose 2 and 3 of Immunotherapy⁵	4-Weeks After End of Radiation⁶	16-Weeks After End of Radiation⁷
Informed Consent	X			
Medical History	X		X	X
Physical Exam	X		X	X
ECOG Performance Status	X		X	X
Blood Draw¹	X	X	X	X
Radiation Therapy		X		
Tumor biopsy (optional)²		X		X
CT C/A/P³	X		X	X

¹Blood draw will consist of 9 tubes: 8 yellow top tubes (BD Vacutainer #364606 Acid citrate dextrose additives ACD Solution A) and 1 red top tube (BD Vacutainer #367820 Clot Activator) to collect and store the following: 1) 6 tubes of 0.5 ml serum; 2) 2 tubes of 1.0 ml plasma; 3) 4 tubes of 0.5 ml PBMC; and 4) 6 tubes of 1 ml PMBC.

²Tumor biopsy of a radiated or non-radiated site will be performed for patients who consent.

³CT C/A/P is preferred but MRI or PET/CT also acceptable.

⁴All pre-treatment assessments must be performed within 30 days of protocol enrollment, except CT C/A/P which must be within 45 days of protocol enrollment.

Pembrolizumab is typically given every 3 weeks. Dose 2 must happen between 2.5-5 weeks after dose 1, and dose 3 must happen between 6-9 weeks after dose 1.

⁶Acceptable date range is 3 to 6 weeks after radiation ends.

⁷Acceptable date range is 12 to 24 weeks after radiation ends.

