6.2 Pembrolizumab Supportive Care Guidelines

Subjects should receive appropriate supportive care measures per standard clinical care as deemed necessary by the treating oncologist. Suggested supportive care measures for the management of adverse events with potential immunologic etiology are outlined below. Where appropriate, these guidelines include the use of oral or intravenous treatment with corticosteroids as well as additional anti-inflammatory agents if symptoms do not improve with administration of corticosteroids. Note that several courses of steroid tapering may be necessary as symptoms may worsen when the steroid dose is decreased. For each disorder, attempts should be made to rule out other causes such as metastatic disease or bacterial or viral infection, which might require additional supportive care. The treatment guidelines are intended to be applied when the oncologist determines the events to be related to pembrolizumab.

- Pneumonitis:
 - For Grade 2 events, treat with systemic corticosteroids. When symptoms improve to Grade 1 or less, steroid taper should be started and continued over no less than 4 weeks.
 - For Grade 3-4 events, immediately treat with intravenous steroids. Administer additional anti-inflammatory measures, as needed.
 - Add prophylactic antibiotics for opportunistic infections in the case of prolonged steroid administration.
- Diarrhea/Colitis: Subjects should be carefully monitored for signs and symptoms of enterocolitis (such as diarrhea, abdominal pain, blood or mucus in stool, with or without fever) and of bowel perforation (such as peritoneal signs and ileus).
 - All subjects who experience diarrhea/colitis should be advised to drink liberal quantities of clear fluids. If sufficient oral fluid intake is not feasible, fluid and electrolytes should be substituted via IV infusion.
 - For Grade 2 or higher diarrhea, consider GI consultation and endoscopy to confirm or rule out colitis.
 - For Grade 2 diarrhea/colitis that persists greater than 3 days, administer oral corticosteroids.
 - For Grade 3 or 4 diarrhea/colitis treat with intravenous steroids followed by high dose oral steroids.
 - When symptoms improve to Grade 1 or less, steroid taper should be started and continued over no less than 4 weeks.
- Type 1 diabetes mellitus (if new onset, including diabetic ketoacidosis [DKA]) or \geq Grade 3 Hyperglycemia, if associated with ketosis (ketonuria) or metabolic acidosis (DKA)

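### Section 7.2 sets expectedness by listing alone, so a listed event is labelled expected at any severity, and even when only the other treatment's list names it

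*Combined protocol and SAP*

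**What the plan says.** Section 7.2 of the protocol makes expectedness a two-way label: "The event will be determined to be expected or unexpected". It names two references. The first is the drug: "The determination of whether an AE is expected is based on pembrolizumab-specific adverse event information per prescribing information". The second is "site specific toxicity listed on radiation treatment consent form for patients receiving radiation treatment". It then defines one side of the label: "Unexpected AEs are those not listed in the agent-specific adverse event information nor radiation consent form".

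Severity is handled as a separate item: "The grade and severity of the event will be determined using CTCAE v.4.0". Relationship is a third item, rated on a four-level scale from unrelated to definite. The three feed one decision: "Based on this information, institutional guidelines will be followed regarding whether an adverse event should be reported as an expedited report". The protocol does not reproduce those guidelines.

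The regimen under test is the combination. Section 3.1 describes the radiation as being given "with the goal being to augment the immune response". Section 6.2 covers immune events already known for the drug: "Suggested supportive care measures for the management of adverse events with potential immunologic etiology are outlined below". It goes on to pneumonitis, colitis, hypophysitis, and hepatic and renal events, among others.

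**The concern.** Each reference list describes a single treatment, but the trial adds radiation in order to strengthen the immune response to the drug. One foreseeable harm of the combination is therefore a familiar event that becomes worse: an immune event known for pembrolizumab, or an in-field radiation effect. A label that asks only whether the event is listed cannot pick out that pattern.

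The label also pools the two lists. An event that the investigator attributes to radiation counts as expected if the pembrolizumab information alone names it, and the reverse holds too.

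At stake is the quality of one input to safety reporting, for a combination with little prior evidence. The Introduction states that clinical data had not been published even for photon radiation with immunotherapy in metastatic bladder cancer.

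**Working it through.** The documents give no figure to reproduce. The check is a reading of the definition, followed by a short calculation of how often it might matter.

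**Step 1: the definition.** Let P mean that the event is in the pembrolizumab information and R that it is on the radiation consent form. Section 7.2 gives: unexpected = not P and not R. Since the label has only two values, expected = P or R. CTCAE grade, outcome and attributed treatment do not appear in either expression.

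**Step 2: a search for another criterion.** Sections 6.2, 7.1, 8, 8.1 and 8.2 contain no other definition of expectedness, and none adds a test of severity, specificity or combination effect.

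**Step 3: the label beside the stopping rule.** Section 8.1 stops the trial for any grade 5 event, or for two or more grade 4 events, within 30 days after the end of treatment and at least possibly related to radiation. It does not use expectedness.

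| Event (listed, by assumption) | Label under 7.2 | Does 8.1 act? |
|---|---|---|
| Grade 5, possibly related to radiation, inside 30 days | Expected | Yes |
| One grade 4, possibly related to radiation, inside 30 days | Expected | No; two are needed |
| Grade 4 or 5 after the 30-day window | Expected | No |
| Grade 4 or 5 judged unrelated to radiation | Expected | No |
| Any grade, attributed to radiation, on the pembrolizumab list only | Expected | Depends on grade, number and timing |

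The first row is covered whatever the label. The next three are where the label could matter. The last shows the pooling of the lists.

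**Step 4: how often.** The inputs are n = 20 evaluable subjects (Study Summary) and an assumed probability p of 2% to 5% that a patient has a grade 4 or 5 event of a listed type that the combination has worsened. The documents give no source for p.

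- Mean number of events = n × p: 20 × 0.02 = 0.4 and 20 × 0.05 = 1.0.
- Chance of at least one = 1 − (1 − p)^n: 1 − 0.98^20 = 0.33 and 1 − 0.95^20 = 0.64.

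Both results include events that 8.1 would catch, so for the residual gap they are too high if the assumed range is right.

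**Step 5: how long review could wait.** Section 8.2 calls for interim reports twice a year (12 / 2 = 6 months apart) and for committee review at least yearly (12 months). These are upper bounds on the wait for scheduled review. They apply only if the event is not expedited and nobody asks for the as-needed review that 8.2 also allows.

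**The case against.** The strongest reply is that expectedness does not decide anything by itself here. Grade and relationship are passed on with it, and the institutional guidelines may expedite every related fatal or life-threatening event or carry their own severity-based definition. Sections 1 and 8.2 also bind the trial to federal and other guidelines. This stands. A reader might infer that a severe listed event would never be expedited, or would always be treated as expected when the report is decided. The documents do not support that: they establish the label, not the outcome.

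Second, neither list is reproduced. If a list states limits of severity, an assessor might treat a worse event as not listed. That is possible, but 7.2 does not say so. The events in section 6.2 are examples from supportive-care guidance, not the reference list.

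Third, the worst case is largely covered. An investigator who suspects that radiation worsened an immune event has in effect judged it at least possibly related to radiation. If it is fatal and inside the window, 8.1 acts. This also stands, and it confines the gap to the cases in Step 3.

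Fourth, the PI hears of grade 4 and 5 events within 24 hours and of grade 3 events within 48 hours, and independent monitoring visits take place. The PI would therefore know promptly. But that is notification within the trial team, and it does not change the label sent on to the reporting decision.

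**Conclusion.** The point holds for the label. As written, 7.2 gives the expedited-report decision an input that takes no account of severity and does not match the list to the attributed treatment. No other section corrects this.

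The consequence is limited. It concerns mainly a single grade 4 event, an event after the 30-day window, or an event not attributed to radiation. Under the assumed 2% to 5%, that is at most 0.4 to 1 event on average in 20 patients, with a 33% to 64% chance of at least one, before subtracting what 8.1 catches. The range is illustrative.

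It would go too far to say that reports would be missed, or that review would in fact be delayed by 6 or 12 months. Either claim depends on guidelines that the documents do not contain and on as-needed review not being called. This is a weakness in a safety definition that is cheap to correct. It does not affect the primary analysis or the validity of the trial.

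**What to change.** Replace the defining sentence in 7.2 with:

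> An AE is unexpected if it is not listed for the treatment to which it is attributed, or if its nature, severity (including fatal outcome) or specificity exceeds what that listing describes. An event judged possibly, probably or definitely related to both treatments is unexpected if it is more severe than either listing describes.

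Two features of this wording matter. A fatal listed event becomes unexpected only where the listing does not describe a fatal outcome, which avoids needless reports. And an event due to both treatments is identified through the existing relationship scale, which has no category for the combination. For this to work, relationship should be rated once for pembrolizumab and once for radiation; 8.1 already presupposes the rating for radiation.

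Also cite in 7.2 the institutional guideline that governs expedited reporting, so that a reader can see how grade, expectedness and relationship are combined.

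The cost is one paragraph and possibly a few more expedited reports: about 0.4 to 1 event in 20 patients under the assumed rate.

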8.1 Early Stopping Rules

Early stopping of this trial will be any grade 5 adverse events (AEs) or multiple (2 or more) grade 4 AEs occurring within ≤ 30 days after the end of treatment defined as possibly, probably, or definitely related to radiation treatment (per CTCAE, v.4.0). All AE's grade 4 or higher must be reported to the PI within 24 hours. All grade 3 AEs must be reported to the PI within 48 hours

8.2 Interim Data Review

Interim reports with statistical analyses will be prepared twice per year until the initial treatment results have been presented or published. In general, the interim reports will contain the following information:

- Patient accrual rate with a projected completion date (while the study is still accruing)
- Total patients accrued
- Frequencies and severity of adverse events
- Compliance rates of treatment delivery

Institutional support of trial monitoring will be in accordance with the FHCRC/University of Washington Cancer Consortium Institutional Data and Safety Monitoring Plan. Under the provisions of this plan, FHCRC Clinical Research Support (CRS) coordinates data and compliance monitoring conducted by consultants, contract research organizations, or FHCRC employees unaffiliated with the conduct of the study. Independent monitoring visits occur at specified intervals determined by the assessed risk level of the study and the findings of previous visits per the institutional DSMP.

In addition, protocols are reviewed at least annually and as needed by the Consortium Data and Safety Monitoring Committee (DSMC), FHCRC Scientific Review Committee (SRC) and the FHCRC/University of Washington Cancer Consortium Institutional Review Board (IRB). The review committees evaluate accrual, adverse events, stopping rules, and adherence to the applicable data and safety monitoring plan for studies actively enrolling or treating subjects. The IRB reviews the study progress and safety information to assess continued acceptability of the risk-benefit ratio for human subjects. Approval of committees as applicable is necessary to continue the study.

The trial will comply with the standard guidelines set forth by these regulatory committees and other institutional, state and federal guidelines.

9 Data Management/Confidentiality

The investigator will ensure that data collected conform to all established guidelines. Each subject is assigned a unique patient number to assure subject confidentiality. Subjects will not be referred to by this number, by name, or by any other individual identifier in any publication or external presentation. The licensed medical records department, affiliated with the institution where the subject receives medical care, maintains all original inpatient and outpatient chart documents.

Subject research files are stored in a secure place (or database). Access is restricted to authorized personnel.

References

